DM consists of three integrated platforms: a mobile app for the patient, a patented movement-tracking algorithm, and a web-based Doctor Dashboard through which the orthodontist receives updates on the patient's progress¹⁴. Using Dental Monitoring's Doctor Dashboard technology, it is possible to quantify and qualify the types of tooth movement occurring during active orthodontic treatment. Crown movements can be traced and analyzed in three axes of translation and three axes of rotation, resulting in nearly 168 measurements for each photo examination, including mesial/distal translation, extrusion/intrusion, buccal/lingual translation, angulation, mesial/distal rotation, and vestibular/lingual torque²⁵. This information can improve the provider's understanding of how teeth move from week to week between adjustments. Using this knowledge, the orthodontist can determine the appropriate time needed between appointments to maximize efficiency in carrying out the treatment plan. Data on how each tooth moves also allows the orthodontist to better plan the mechanics required at subsequent appointments. A thorough understanding of tooth movement can reduce treatment time and optimize the number of office visits, greatly reducing cost to both patient and provider.

A study by Moylan et al.²⁶ examined the accuracy of photos taken by the patient as compared to those taken by a provider and determined that there is no statistically significant difference in the quality of scans taken by patients versus providers. It also found that the accuracy of DM's measurements was sufficient for use in clinical practice with average absolute differences of less than 1mm when comparing DM scans to plaster models. Morris et al.²⁷ examined the accuracy of DM scans as compared to iTero Element scans using typodonts and determined the 3D digital models generated by DM to be accurate enough for clinical application.

The study by Moylan et al.²⁶ evaluated the accuracy of the DM system in a model of rapid maxillary expansion. The study tried to evaluate if the tooth movement magnitudes captured with the DM videos and photographs were accurate when measured against intraoral scans taken with the iTero scanner. Another tooth movement model to be tested is the canine retraction model. DM has not been evaluated on the accuracy of measuring canine tooth movement during space closure.

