Canine retraction for space closure after premolar extraction is an excellent model to evaluate rate of tooth movement. Clinical trials with surgical and non-surgical methods of tooth movement acceleration have relied on this tooth movement model to test the efficiency of the different approaches. However, a detailed understanding of the rate of canine retraction and the overall nature of tooth movement is missing in the orthodontic literature. In fact, recently Nickel et al.²⁸ found that canine retraction did not follow the conventional tooth movement phases that have been reported in the literature. Specifically, they reported that a majority of subjects in their study appeared not to have a lag phase and tooth movement appeared to be a continuous process. DM offers a unique opportunity to track the type of tooth movement and magnitude of tooth movement at intervals much shorter than a monthly visit, without the patient needing to visit the provider.

The objective of this study is to test the accuracy of the DM software in determining the precise tooth movements during 5-6 weeks of canine retraction. Furthermore, a description of the magnitude of tooth movement on a biweekly basis will start to provide better information on the nature of the biology of tooth movement. Determining which periods of tooth movement are more significant during the 5-6 weeks of evaluation may help elucidate what the ideal time interval is for patient visits and maximize treatment efficiency. Furthermore, the data could help determine, at an early stage, which patients will be fast and slow movers during orthodontic treatment.

Hypothesis, Aims and Objectives:

- **Null Hypothesis:** There is no significant difference in accuracy of digital scans between the Dental Monitoring and iTero groups in a maxillary canine retraction model.
- **Aims/Objectives**
 - Primary Objective: To evaluate the accuracy and reliability of Dental Monitoring scans to that of iTero digital scans during maxillary canine retraction.
 - Secondary Objective: To quantify the magnitude and type of tooth movement occurring in a 5-6 weeks period in patients undergoing maxillary canine retraction.

Study Design:

- **Study design:** Prospective clinical trial, pilot study
- **Sample size:** 40 patients

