- **Sample size justification:** There has been no study evaluating the accuracy of canine retraction with this software. This will be a pilot study from which preliminary data will be obtained for a larger study.

- **Method of data gathering:** Patients undergoing orthodontic treatment in the Center for Orthodontic Care at UConn Health will be evaluated for the inclusion criteria. A total of twenty patients whose orthodontic treatment plan required extraction of at least one premolar in the maxillary arch will be recruited. The patient will be required to take photographs and video scans as dictated by Dental Monitoring (DM) on the first and final days of the study period (five weeks), while iTero scans are taken by the provider in clinic on these same days. The patients will also be asked to take photograph and video DM scans every 4 days during the 5-6 weeks period. DM will provide cheek retractors and scan boxes, which are FDA approved, and the patient will be instructed on how to use the devices to procure photographs and videos.
- **Method of measuring accuracy:** Compare the DM scans taken by the patient to iTero digital scans taken by the provider. This can be done by superimposing the stereolithographic (STL) files created from each scan and assessing the amount of deviation between the 3D models.
- **Method of measuring tooth movement:** Quantify the types of tooth movement occurring during canine retraction in buccolingual, mesiodistal, and incisogingival planes using Doctor Dashboard software available in DM. DM's 3D matching technology allows superimposition of teeth from each 3D model created per scan. Each tooth and its movements are graphed in a detailed manner to provide precise information about its type of movement.
- **Confidentiality of data/privacy of subjects:** Each subject will be assigned a code; the correlation will be denoted in a master list, which will be kept in a locked file cabinet, only accessible to the study coordinator and principal investigator.

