- **Data Safety Monitoring:** The investigator and study coordinators will perform safety monitoring to ensure that risks to subjects are minimal. Serious adverse events associated with routine orthodontic treatment are rare. If any such unanticipated events occur, their provider(s) will provide any necessary clinical/palliative treatment to subjects. An assigned orthodontic resident is always on-call and available to provide such treatment and the study team will be available for consultation. Report of the event will be made to the IRB within 5 days of becoming aware of the occurrence.
- **Additional protections for vulnerable populations:** This study will likely include minors as subjects. As detailed in Form D, additional protections will be taken for this population, including obtaining assent from the subject and permission from a parent/guardian. This study does not involve greater than minimal risk.

➤ **Outcome Variables**

- **Primary Outcome:** There is no significant difference in accuracy or reliability between patient-taken DM scans and provider-taken iTero scans at the maxillary canine.

- **Secondary Outcome:** DM scans allow for precise tracking of tooth movement, which can help optimize treatment. Knowledge gained from this study and future treatment studies regarding the quantity and type of tooth movement occurring in canine retraction cases will allow the provider to be better able to customize subsequent appointments. This will allow for more efficient treatment and potentially reduced treatment time and cost in future patients.

Subject Characteristics: All subjects will have permanent dentition; Ethnicity: N/A; Gender: male and female; Other characteristics: undergoing fixed orthodontic treatment with extraction plan.

➤ Inclusion Criteria

- Male and female
- Patients with fixed orthodontic appliances, in 19x25 SS, using NiTi coil for canine retraction
- Treatment plan requiring extraction of at least one maxillary premolar
- Permanent dentition from first molar to first molar in the maxilla
- Teeth with normal crown morphology
- Fully erupted canines
- Above 11 years of age
- Patients with any cellular phone with a camera

➤ Exclusion Criteria

- Lack of extraction in orthodontic treatment plan
- Previous canine retraction
- Syndromic patients
- Cleft lip/palate patients
- Removable appliances

Recruitment

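### The introduction sets out to test how accurately Dental Monitoring measures canine movement, but the plan compares only Dental Monitoring and iTero models and specifies no movement comparison

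*Combined protocol and SAP*

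**What the plan says.** The combined protocol and SAP gives two accounts of what is to be tested.

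- **Movement accuracy.** The introduction names the gap: "DM has not been evaluated on the accuracy of measuring canine tooth movement during space closure". It then gives the objective as to "test the accuracy of the DM software in determining the precise tooth movements during 5-6 weeks of canine retraction".
- **Scan agreement.** The primary objective is "To evaluate the accuracy and reliability of Dental Monitoring scans to that of iTero digital scans during maxillary canine retraction". The primary outcome, under Outcome Variables, is "There is no significant difference in accuracy or reliability between patient-taken DM scans and provider-taken iTero scans at the maxillary canine". The null hypothesis is also about digital scans. The method of measuring accuracy, under Study Design, reads "This can be done by superimposing the stereolithographic (STL) files created from each scan and assessing the amount of deviation between the 3D models". It names no registration area.

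Movement itself is quantified in three planes "using Doctor Dashboard software available in DM", by superimposing DM models on one another. The secondary outcome is worded as a finding: "DM scans allow for precise tracking of tooth movement, which can help optimize treatment".

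Under Study Procedures, each patient contributes two DM and two iTero scans, on day 1 and the final day, for the accuracy analysis. DM scans every 4 days serve the second objective. No section derives a canine displacement from the two iTero scans.

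**The concern.** Accuracy of a model on a given day and accuracy of movement between two days are different quantities. The second depends on how the errors on the two days relate to each other, and on how the software turns its models into reported displacements. The planned analysis looks at neither.

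The introduction hopes to use the movement data to judge visit intervals and to identify fast and slow movers, and those uses need credible movement values. The pilot is also meant to supply preliminary data for a larger study. As written, it would give no estimate of the spread of the DM-minus-iTero movement difference, which a larger study of movement accuracy would need for planning.

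**Working it through.** The documents state no figure on this point (no SD, margin, alpha or power), so there is nothing to reproduce. The check is a comparison of sections, followed by illustrations in unknown units.

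**1. What is compared with what**

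| Element | Quantity | Compared with iTero? |
|---|---|---|
| Introduction: gap and objective | Canine movement | Implied |
| Null hypothesis, primary objective, primary outcome | Scans | Yes |
| Method of measuring accuracy | Deviation between models | Yes |
| Method of measuring tooth movement | Dashboard movement | No |
| Secondary outcome | Precise tracking, asserted | No |

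**2. Does model agreement settle movement accuracy?** Let e1 and e2 be the DM-minus-iTero canine position errors on day 1 and the final day, in a frame common to both days. Movement error is e2 − e1. With equal SD s and correlation r (both assumed), its SD is s√(2(1−r)):

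- r = 0.9: 0.45s
- r = 0.5: 1.00s
- r = 0: 1.41s
- r = −1, the extreme: 2s

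An illustration with assumed values: errors of +0.3 mm on both days give a mean absolute deviation of 0.3 mm and a movement error of 0. Errors of +0.3 mm and then −0.3 mm give the same 0.3 mm deviation and a movement error of 0.6 mm in size. Agreement therefore bounds movement error without fixing it. This concerns the models; the dashboard's displacement output is a further step that agreement does not test.

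**3. Effect of the unspecified registration.** Assume a translation-only, equal-weight best fit on k teeth, with c canines each off by e. The error left visible at the canine is e(1 − c/k). The inclusion criterion "Permanent dentition from first molar to first molar in the maxilla" means at least 12 teeth before extraction, so take 11 or 10 after one or two premolar extractions (an assumption).

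- k = 11, c = 1: 10/11 = 0.91e
- k = 10, c = 2: 8/10 = 0.80e
- With two second molars added (k = 13 or 12): 12/13 = 0.92e or 10/12 = 0.83e
- Fit on the canine alone (k = 1, c = 1): 0

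A full-arch fit thus hides about 8% to 20% of the canine error in this simple model. Only a canine-only fit, which no section proposes, hides all of it.

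**4. What the existing scans can check.** The two iTero scans can yield the day-1-to-final total only. Over 35 days, 4-day scanning gives 8 full intervals plus 3 days, or 9 intervals. Over 42 days it gives 10 full intervals plus 2 days, or 11. None of these has an iTero scan at both ends, and neither do the biweekly summaries that the introduction plans.

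**5. Precision of an added movement comparison.** This is not a measure of the defect. Let d be the unknown SD of the displacement difference, with one canine per patient and complete scans. The 95% half-width for bias is t(n−1)·d/√n. For each limit of agreement it is t(n−1)·d·√(1/n + 1.96²/(2(n−1))).

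- n = 20: 2.093/4.472 = 0.47d for bias; 0.81d for each limit
- n = 40: 2.023/6.325 = 0.32d for bias; 0.55d for each limit

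Study Design gives both sample sizes: 40 in the sample-size line, and twenty under the method of data gathering.

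**The case against.** The best defence is that the formal elements agree with one another. The null hypothesis, primary objective, primary outcome and accuracy method all concern scans, the secondary objective is to quantify rather than validate, and this is a pilot. That stands, and a reader should not infer that the formal objectives contradict each other. The conflict is between them and the introduction's rationale and objective, and between the descriptive secondary objective and a secondary outcome that asserts precision.

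Two stronger readings are tempting.

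- **That no reference for movement exists.** The documents do not support this. Day-1 and final iTero scans are collected, the introduction says movement can be mapped by superimposing models on stable structures, and it describes an earlier expansion study that set DM movement magnitudes against iTero scans. For total movement, what is missing is a planned comparison rather than data.
- **That registering on a region that includes the canine makes the agreement result worthless.** It does not. Under the simple model most of the error stays visible, and the tooth count used is a minimum.

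It is also fair to say that the practical size of the problem in millimetres cannot be given. The introduction reports average absolute differences below 1 mm against plaster models as clinically sufficient. This study does not adopt that as a criterion, and it is not a canine-displacement figure.

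**Conclusion.** The concern holds as a mismatch between the stated objective and the planned analysis, and it should be fixed. As written, the pilot could report good scan agreement without having tested DM's accuracy in measuring canine movement, and without support for the claim of precise tracking.

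The mismatch itself rests on the text alone. Its size can be expressed only relative to unknowns: a movement-error SD between 0.45s and 1.41s for r between 0.9 and 0, assuming equal error SD on both days and a common frame. The registration gap is secondary and, for a full-arch fit, modest. Confidence is high for the mismatch. It is lower for the main remedy, because the documents describe neither the stable structures to be used nor the dashboard's reference frame.

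**What to change.** 1. Keep the scan-agreement outcome, and specify it as paired by day, assessed at the canine crown and registered on teeth other than the canine.
2. Add a prespecified movement-accuracy analysis: the per-canine difference between DM's day-1-to-final displacement and the displacement from the two iTero models superimposed on named stable structures, for each of the buccolingual, mesiodistal and incisogingival axes. State how DM and iTero axes are aligned. Report bias and 95% limits of agreement with confidence intervals, allowing for two canines in one patient.
3. State that this checks the total only, so that the 4-day and biweekly movement descriptions remain unvalidated.
4. If stable structures or axis alignment are unavailable, align the introduction's objective with scan agreement, reword the secondary outcome so that it does not assert precise tracking, and label dashboard movement as unvalidated.
5. Reconcile the two sample sizes, since they determine the precision of the added analysis.

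The cost is one extra superimposition of the two iTero models per patient, the alignment work and protocol wording. No new visit, scan or procedure is needed. The fallback in item 4 costs wording only.

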A recently invented technology, Dental Monitoring (DM), allows orthodontists to monitor their patients remotely, using photographs or video scans taken by patients via smartphone. From this data, it can construct three-dimensional (3D) digital models.^{14,15} With continuing advances in 3D digital imaging technology, conventional impression materials and dental stone casts are being replaced by digital impressions captured by intraoral scanners.^{16,17} Digital models do not require disinfection and can be readily modified through computer software for more in-depth examinations of individual teeth and intra/interarch relationships. 3D mapping of tooth movement is achievable by superimposing digital models on stable structures with 3D software systems.¹⁸⁻²⁰ With the trend toward digital impressions, recent studies have focused on evaluating the accuracy of digital scanners.²⁰⁻²⁴ Digital impressions captured by intraoral scanners have been shown to be as accurate, in both trueness and precision, as conventional elastomeric impressions, and thus are acceptable for clinical use.²²⁻²⁴ Numerous studies have tested the accuracy of full-arch iTero (Align Technology, San Jose, Calif) generated digital models and demonstrated good results.

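### The null hypothesis and primary outcome frame DM accuracy and reliability as no significant difference from iTero, with no scored deviation, agreement statistic or limit; a non-significant result would not show agreement

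*Combined protocol and SAP*

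**What the plan says.** Under Hypothesis, Aims and Objectives, the null hypothesis is "There is no significant difference in accuracy of digital scans between the Dental Monitoring and iTero groups" in a canine retraction model, and the primary objective is "To evaluate the accuracy and reliability of Dental Monitoring scans to that of iTero digital scans during maxillary canine retraction". Under Outcome Variables, the primary outcome is "There is no significant difference in accuracy or reliability between patient-taken DM scans and provider-taken iTero scans at the maxillary canine".

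Under Study Design, the method of measuring accuracy is to superimpose the STL files from the DM and iTero scans and assess how far the models deviate. No summary of that deviation is named (signed, absolute or root mean square), nor any unit, test, confidence interval, agreement statistic or acceptable limit. The combined document has no statistical analysis section. Reliability is not defined.

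Under Study Procedures, the accuracy analysis has two DM and two iTero scans per patient, one of each on the first and final days. Further DM scans are taken every 4 days for the secondary objective.

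Three statements in the Introduction also bear on the point:
- The study aim is given as "to test the accuracy of the DM software in determining the precise tooth movements during 5-6 weeks of canine retraction".
- Intraoral scans are described as "shown to be as accurate, in both trueness and precision, as conventional elastomeric impressions", so the document itself treats accuracy as having two parts.
- The only numerical accuracy figure, "average absolute differences of less than 1mm when comparing DM scans to plaster models", is a background result from another study.

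**The concern.** Failing to reject a hypothesis of no difference is not evidence that two methods agree. It can come from good agreement, from large scatter or from few patients. If the primary outcome is taken as worded, a biased or noisy DM system could be reported as accurate.

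There is also a problem of definition. If iTero is the reference, each superimposition yields a single DM-iTero deviation. There is no separate accuracy value for DM and another for iTero, so there are no two groups whose accuracy could be compared.

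The study is described as a pilot supplying preliminary data for a larger one. That larger study will need the size of the bias and scatter and how precisely each is known. A non-significant p-value gives none of these.

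**Working it through.** **Inputs.** The documents give no alpha, SD, bias, margin or power, so there is no planned figure to reproduce. All biases, SDs and cut-offs below are assumptions that illustrate the principle; they do not measure this study's risk. Assumed: one DM minus iTero difference per patient, normally distributed; two-sided 5% paired t-test. Both n = 20 and n = 40 are shown because the sample size line says 40 while the data-gathering text says "A total of twenty patients whose orthodontic treatment plan required extraction of at least one premolar in the maxillary arch will be recruited". That conflict is a separate matter.

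**1. Signed differences.** The non-centrality is bias/SD × √n. The critical t is 2.093 (19 df) or 2.023 (39 df). For bias 0.5 mm and SD 1.0 mm the non-centrality is 0.5 × √20 = 2.24 or 0.5 × √40 = 3.16. The chance of a non-significant result, from the non-central t, is:

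| True bias | SD | n = 20 | n = 40 |
|---|---|---|---|
| 0.5 mm | 0.5 mm | 1.1% | 0.0% |
| 0.5 mm | 1.0 mm | 43.5% | 13.1% |
| 0.5 mm | 2.0 mm | 81.4% | 66.2% |
| 0 | any | 95% | 95% |

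With a real bias, more scatter or fewer patients makes non-significance more likely. At zero bias the rate is 95% by construction and does not change with scatter, although agreement does. The mean absolute deviation is SD × √(2/π), which is 0.40, 0.80 and 1.60 mm at SD 0.5, 1.0 and 2.0 mm. The share of differences beyond an illustrative 1 mm is 5%, 32% and 62%. The test does not register this.

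**2. Absolute deviations tested against zero.** At zero bias the mean of the absolute values is 0.798 SD and their standard deviation is √(1 − 2/π) = 0.603 SD. The expected t is about (0.798/0.603) × √n = 5.9 at n = 20 and 8.4 at n = 40, far beyond the critical values. In 100,000 simulated trials per cell (bias 0, 0.25 and 0.5 mm; SD 0.5, 1.0 and 2.0 mm; both n), non-significance occurred 0.0% of the time in every cell. Root mean square deviations were not simulated, but they too are positive whenever the models differ at all, so the same reasoning applies.

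**3. Consequence of the scoring.** At zero bias the same scans give a non-significant result 95% of the time if signed and essentially never if absolute.

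**4. What estimation would give.** Half-widths of 95% intervals, in units of the SD of the differences:

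| Quantity | Formula | n = 20 | n = 40 |
|---|---|---|---|
| Mean bias | t/√n | 0.47 | 0.32 |
| Each limit of agreement | t√(1/n + 1.96²/(2(n − 1))) | 0.81 | 0.55 |
| Mean absolute deviation (zero bias) | t√(1 − 2/π)/√n | 0.28 | 0.19 |

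**5. Reliability.** Each device contributes one scan per time point. The 4-day DM scans are taken while the canine is being moved, so differences between them mix true movement with measurement error. Scan repeatability cannot be separated out.

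**The case against.** The strongest reply has three parts.

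First, the primary outcome may be an anticipated finding rather than a decision rule. The secondary outcome beside it is also written as an expected benefit, and no test, alpha or pass rule appears anywhere. This stands in part: the harm is conditional on how the wording is used. But on that reading the protocol has no primary outcome measure, and the null hypothesis still has the same form.

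Second, the protocol does name a direct DM-to-iTero quantity. This also stands. A reader might infer that the plan has no measure of agreement at all, and the accuracy method does not support that. What is missing is its scoring, a summary with an interval, and a limit.

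Third, a reader might infer that noisier DM scans always make the stated outcome easier to reach. The documents do not support that either, because they specify no test. It holds only if signed differences are tested and DM is biased. At zero bias scatter makes no difference, and with absolute deviations tested against zero the effect disappears.

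The pilot label excuses the absence of a power calculation. It does not excuse an accuracy conclusion drawn from non-significance.

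**Conclusion.** The point holds in this form: the null hypothesis and primary outcome use a comparison that is not well defined for one deviation per scan pair, that cannot show agreement when non-significant, and whose result could turn on an unstated scoring choice. This follows from the wording and needs no assumed value.

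The size is illustrative only. At an assumed bias of 0.5 mm, signed testing would miss the bias 44% (n = 20) or 13% (n = 40) of the time at SD 1.0 mm, and 81% or 66% at SD 2.0 mm. The documents do not show that DM is inaccurate, or that the investigators have chosen this test.

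The wording should be corrected before analysis, since it sits in the primary outcome and a better analysis is available from scans already scheduled.

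**What to change.** Replace the null hypothesis and primary outcome with estimation of agreement, taking iTero as the reference.

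- **Primary analysis.** State how the DM-to-iTero deviation at the canine is scored at each time point. Report the mean absolute or root mean square deviation with its 95% confidence interval. If the deviation is signed, also report mean bias and 95% Bland-Altman limits of agreement, each with confidence intervals. Allow for two canines and two time points in one patient, by a mixed model or a patient-level bootstrap.
- **Optional addition.** Because the Introduction gives the aim as accuracy in determining tooth movement, also report bias and limits of agreement for DM minus iTero canine movement from the first to the final day, with one direction named as primary. This depends on whether the existing iTero scans can be superimposed on stable structures. The Introduction says in general that "3D mapping of tooth movement is achievable by superimposing digital models on stable structures with 3D software systems", but the protocol does not say these scans will capture suitable structures.
- **Reliability.** Limit it to DM-iTero agreement, or to repeatability of the superimposition measurement on existing files.
- **Claims.** Report the pilot as estimation only. Claim adequacy only against a justified tolerance in mm and a named quantity that must lie inside it, both fixed beforehand. The background figure of under 1 mm should not be adopted by default: it is an average absolute difference against plaster models, and with zero bias and SD 1.0 mm that average would be 0.80 mm while 32% of values are off by more than 1 mm.

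The cost is revised wording and a little more analysis, with no new patients or scans. The optional movement comparison needs added measurement on the iTero files. The conclusion may be less favourable.
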